7.3.8 Sodium intake

- Outcome: Continuous outcome of urinary sodium concentration (mmol/24 hours) in lactating women.
- Primary analysis: Descriptive means and standard deviation of urinary sodium concentration in a subset of 100 lactating women.

7.3.9 Mullen (composite and 5 subscales)

- Outcome: Continuous outcomes of Composite Mullen and the 5 subscales of the Mullen at 24 and 52 weeks postpartum.

Primary analysis: Test for a treatment effect using a separate linear regression model for each outcome and estimate a difference in means (positive control minus placebo).

Adjustment: Mullen scales at 2 and 12 weeks postpartum and health centre

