The full statistical analysis plan can be found in **Appendix B**. The primary analyses will be performed on an ‘intention to treat’ basis, where all participants will be analyzed according to their allocated treatment group regardless of compliance. A secondary ‘per-protocol’ analysis will be performed on the subset of women who consumed $\geq 80\%$ capsules over the study period. The parameters of the Emax dose-response curves will be estimated using non-linear least squares models. Separate curves will be fitted for outcomes measured at 4 weeks, 12 weeks, and 24 weeks postpartum. The dose where additional maternal intake of thiamine no longer meaningfully increases milk thiamine concentration, defined as the dose that achieves 90% of the maximum concentration, will be estimated from the fitted curve with standard errors estimated by bootstrapping for calculating 95% confidence intervals.

Comparisons between treatment groups will be performed using linear mixed-effects models to account for repeated measurements and adjusted for randomization strata and levels at 2 weeks postnatal. Interaction tests will be performed to assess whether treatment effects depend on genetic hemoglobin disorder. Missing data will be addressed using multiple imputation to create 100 complete datasets for analysis, with a sensitivity analysis performed on the raw (unimputed) data (68). All analyses will follow a pre-specified statistical analysis plan (see **Appendix B**).

12. Administrative Aspects, and Data Security and Management

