3.3 Treatment groups

Participants are randomised to receive supplements containing one of the following:

1. 0 mg thiamine (placebo, negative control group)
2. 1.2 mg thiamine as thiamine hydrochloride (EAR group)
3. 2.4 mg thiamine as thiamine hydrochloride (double EAR group)
4. 10 mg thiamine as thiamine hydrochloride (positive control group)

The supplements will be packaged in 14-capsule blister packs delivered to participants every two weeks. Participants will be asked to consume one capsule per day from 2 weeks to 24 weeks postpartum.

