5.6 Covariates for adjustment

Both unadjusted and adjusted analyses will be performed for some outcomes. Conclusions for these outcomes will be drawn from the adjusted analyses, with unadjusted analyses performed for completeness and to potentially confirm the results of the adjusted analyses.

All adjusted analyses will be adjusted for health centre, since it was used as a stratification variable in the randomisation process. Adjustment will also be made for additional variables collected at 2 weeks postnatal which are potential confounders for some outcomes and these have been identified a priori (see Section 7).

If convergence is an issue, some potential confounders may be excluded from the adjusted analysis. Any deviation from the planned adjustment covariates will be documented in the final report.

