7 STATISTICAL ANALYSES

In this section, the following details are provided for each outcome variable that will be analysed to address the study objectives specified in Section 2:

- **Outcome:** A detailed description of the outcome variable, including the type of variable and how it will be calculated (if applicable).
- **Analysis:** The type of statistical analysis to be performed and parameters to be estimated.
- **Adjustment:** Where relevant, the covariates at 2 weeks postnatal (stratification variables and potential confounders) to adjust for in the adjusted analysis.

For each outcome variable, parameter estimates will be accompanied by 95% two-sided confidence intervals and statistical significance will be assessed at the 0.05 level using a two-sided test, unless otherwise specified.

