- Secondary analyses: First, fit an Emax curve using nonlinear least squares approach allowing curve to vary by presence/absence of genetic hemoglobin disorder. Estimates of the dose that reaches 90% concentration by genetic hemoglobin disorder status will be reported following evidence from the global test. Second, test for a treatment effect using linear regression and estimate a difference in mean concentration. Third, test for a treatment effect using linear regression with treatment group and treatment by genetic hemoglobin disorder interaction. Treatment effects (difference in mean concentration) will be estimated separately by genetic hemoglobin disorder where the relevant interaction term has a p-value <0.05. Pairwise comparisons will be reported following evidence of a treatment group effect (see Section 5.8). Fourth, test for a linear relationship using linear mixed effects model with CRP at 2 and 24 weeks postnatal, time and treatment group as predictors. Estimate of the mean change (with 95% CI) in ThDP for one unit increase in CRP will be reported. Fifth, test for a linear relationship using linear mixed effects model with AGP at 2 and 24 weeks postpartum, time and treatment group as predictors. Estimate of the mean change (with 95% CI) in ThDP for one unit increase in AGP will be reported.
- Adjustment: Maternal ThDP at 2 weeks postpartum, health centre (linear regressions and mixed effects models only)

7.3.5 *Maternal transketolase activity coefficient (24 weeks)*

- Outcome: Continuous outcome of maternal TKac at 24 weeks postpartum.
- Primary analysis: Fit an Emax curve using nonlinear least squares approach. Estimate of the dose that reaches 90% concentration (with 95% CI) will be reported.

- Secondary analyses: First, fit an Emax curve using nonlinear least squares approach allowing curve to vary by presence/absence of genetic hemoglobin disorder. Estimates of the dose that reaches 90% concentration by genetic hemoglobin disorder status will be reported following evidence from the global test. Second, test for a treatment effect using linear regression and estimate a difference in mean TKac. Third, test for a treatment effect using linear regression with treatment group and treatment by genetic hemoglobin disorder interaction. Treatment effects (difference in mean TKac) will be estimated separately by genetic hemoglobin disorder where the relevant interaction term has a p-value <0.05.

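### SAP 7.3.9 adjusts the Mullen treatment effect for a score taken 10 weeks into treatment; separately, SAP 7.3.4 leaves unclear whether 2-week ThDP is an outcome, a covariate or both in the CRP/AGP models

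*Combined protocol and SAP*

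**What the plan says.** **Mullen.** SAP 7.3.9 fits a separate linear regression to the Mullen composite and each of its five subscales at 24 and 52 weeks, to test and estimate the 10 mg versus placebo effect. Its adjustment line reads "Mullen scales at 2 and 12 weeks postpartum and health centre". On timing, SAP 3.3 states: "Participants will be asked to consume one capsule per day from 2 weeks to 24 weeks postpartum".

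The general rules differ from that line. SAP 5.6 says "Adjustment will also be made for additional variables collected at 2 weeks postnatal which are potential confounders for some outcomes". The opening of SAP Section 7 defines the adjustment entry as "Where relevant, the covariates at 2 weeks postnatal (stratification variables and potential confounders) to adjust for in the adjusted analysis". Protocol Section 11 describes group comparisons as "adjusted for randomization strata and levels at 2 weeks postnatal", but in a sentence about mixed models for repeated measurements, so it only supports the point. SAP 5.6 also says "Both unadjusted and adjusted analyses will be performed for some outcomes", without naming Mullen, and "Conclusions for these outcomes will be drawn from the adjusted analyses, with unadjusted analyses performed for completeness and to potentially confirm the results".

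**Inflammation and maternal ThDP.** The SAP 7.3.4 outcome line names maternal ThDP at 24 weeks only. Its fourth secondary analysis is to "test for a linear relationship using linear mixed effects model with CRP at 2 and 24 weeks postnatal, time and treatment group as predictors"; the fifth does the same with AGP. The adjustment line adds 2-week maternal ThDP and says that this applies to the mixed models as well as the linear regressions. SAP objective 6a and Protocol secondary objective 16 ask about the effect of inflammation on maternal ThDP at both 2 and 24 weeks.

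**The concern.** **Mullen.** A covariate that treatment can change is not a baseline adjustment. If thiamine has affected development by week 12, conditioning on the 12-week score removes part of the effect that the comparison is meant to measure. Where both adjusted and unadjusted analyses are run, the adjusted one decides, so the attenuated figure would be the reported conclusion. The 7.3.9 line is the only adjustment line in Section 7 that lists a value measured after baseline, and the SAP neither explains it nor states a direct-effect question.

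**Inflammation models.** If the response includes the 2-week visit, then in those rows the covariate and the outcome are the same number. The model explains those rows perfectly from the covariate and leaves the inflammation slope too little to explain.

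**Working it through.** **1. Timing.** Treatment runs from 2 to 24 weeks and the first blister pack is given at the 2-week visit (Protocol 8.3). The 12-week visit has a window of ±4 days (Protocol 12.5). It therefore falls 12 − 2 = 10 weeks into a 22-week course, always after randomisation.

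**2. What the documents give.** There is no sample size, effect size or correlation for Mullen. The one sample size is for milk thiamine: difference 40, SD 43, two-sided alpha 0.0083 and 90% power give 38 per group by the t-test, and 38/0.8 = 47.5, so 48, as stated. For illustration I carry over its 20% attrition: 80 × 0.8 = 64 per arm.

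**3. Mullen bias.** In SD units, let d12 and dL be the effects at 12 weeks and later. The adjusted coefficient estimates dL − b12 × d12, where

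b12 = [r(12,L) − r(2,12) × r(2,L)] / [1 − r(2,12)²].

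Assumed: r(2,12) = 0.3, r(2,24) = 0.2, r(12,24) = 0.3 to 0.6.

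- r(12,24) = 0.3: (0.3 − 0.06)/0.91 = 0.26
- r(12,24) = 0.6: (0.6 − 0.06)/0.91 = 0.59

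The shortfall is b12 × d12/dL: 0% with no 12-week effect, 7–15% if a quarter of the effect is present, 13–30% if half, 26–59% if all. At 52 weeks, with r(2,52) = 0.1 and r(12,52) = 0.2 to 0.5, b12 is (0.2 − 0.03)/0.91 = 0.19 to (0.5 − 0.03)/0.91 = 0.52, so 9–26% (half) and 19–52% (all).

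**4. Mullen power at 24 weeks, true effect 0.5 SD, two-sided 0.05.** Without the 12-week score the residual variance is 1 − 0.2² = 0.96, SE = √(2 × 0.96/64) = 0.173, and 0.5/0.173 = 2.89, giving 82%. With it, the residual variance is 0.897 (r = 0.3) to 0.640 (r = 0.6), and the variance of the estimate (not its SE) is multiplied by 1 + d12²/[4(1 − r(2,12)²)]. Worked cell, all of the effect present, r = 0.6: estimate 0.5 × (1 − 0.593) = 0.203; SE = √(2 × 0.640/64 × 1.069) = 0.146; ratio 1.39; power 28%.

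| Share of effect present at 12 weeks | Power with 12-week score | Wider correlations |
|---|---|---|
| None | 85–94% | 84–96% |
| Quarter | 80–85% | 78–89% |
| Half | 69–73% | about 64–77% |
| All | 28–57% | 16–64% |

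The last column lets r(2,12) run over 0.1–0.5 and r(2,24) over 0.1–0.3, which widens b12 to 0.20–0.73. Simulation of the regression (4,000 trials per cell) agrees: at r = 0.3 with half of the effect present, mean estimate 0.43 and power 72%.

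**5. Which response do the inflammation models have?** For 24 weeks only: the outcome line. For 2 and 24 weeks: objective 6a, Protocol objective 16, CRP or AGP taken at both visits, and a time term, which has nothing to estimate in a one-visit response. The infant analysis in SAP 7.3.1 has one visit and uses plain regression without time. Maternal ThDP is measured at 2 weeks (Protocol 9.8).

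**6. Consequence on the two-visit reading.** Let ρ be the marker's correlation between visits, R the within-woman ThDP correlation, and s the 24-week ThDP SD divided by the 2-week SD. With the random-intercept variance at zero, where the fit goes in 97–100% of simulated trials, the small-slope share kept is

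1 − (1 + ρ)(1 + R × s)/4.

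With ρ from 0 to 0.6 and R from 0.3 to 0.7 (assumed):

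- s = 1: 1 − 1.6 × 1.7/4 = 0.32 to 1 − 1.3/4 = 0.68
- s = 0.5: 1 − 1.6 × 1.35/4 = 0.46 to 1 − 1.15/4 = 0.71
- s = 2: 1 − 1.6 × 2.4/4 = 0.04 to 1 − 1.6/4 = 0.60 (about 0.05 to 0.62 at slopes that are not negligible)

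Fitted mixed models with true slope −0.20, ρ = 0.3, R = 0.5, s = 1 returned −0.10 with the covariate and −0.20 without it. At zero slope, simulation showed no bias and a type I error of 3–6%.

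**The case against.** **On Mullen**, the strongest reply is that the 12-week score may be a good predictor, that nothing in the documents shows a cognitive effect by then, and that without one the covariate is harmless and raises power from 82% to 85–94%. That is correct, and it is the real price of the fix. But it makes the validity of a treatment comparison depend on the absence of an early treatment effect, which a randomised comparison need not assume. A reader might infer that the Mullen results are bound to be biased. The documents do not support this: the bias is nil without a 12-week effect, and the estimate is too small only if the early and later effects have the same sign. Unadjusted Mullen analyses, if they are among the unnamed outcomes in SAP 5.6, would be free of the problem and could reveal it, but their role is only to confirm.

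**On 7.3.4**, a reader might infer that the SAP definitely puts the same value on both sides of the model. The documents do not settle that. The outcome line says 24 weeks, for which 2-week ThDP is a proper baseline covariate, and one adjustment line serving several models may simply be too broad. SAP 5.6 also allows covariates to be dropped for convergence problems. A zero variance estimate is not strictly non-convergence, but it is a visible warning, so this is a partial mitigation. Nor can one say that the slope will be a third to two thirds of its true size: that range needs equal ThDP spread at both visits, and the documents give neither SD. A claim of false positives would also be wrong, since the test at zero slope stays valid.

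**Conclusion.** The Mullen adjustment is wrong as written, with high confidence: it contradicts SAP 5.6 and the opening of Section 7, and it does not estimate the total treatment effect unless treatment has no effect at 12 weeks. How much this matters cannot be found from the documents. The sizes above rest on assumed correlations, an assumed 0.5 SD effect and attrition borrowed from the milk calculation.

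The 7.3.4 point is separate and held with medium confidence. The weight of the text favours a two-visit response. On that reading a non-zero CRP or AGP slope would keep about 0.32–0.68 of its size with equal ThDP SDs, and about 0.05–0.71 if the 24-week SD is half to twice the 2-week SD.

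Both points concern secondary analyses, to which SAP 5.8 gives less weight. VPC, Language Preference, oculomotor scores, infant ThDP, the 24-week maternal treatment regressions and the primary analysis are not affected. The change should be made but does not threaten the trial's main result.

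**What to change.** **SAP 7.3.9:** adjust for 2-week Mullen and health centre only. The 12-week score can remain an auxiliary variable in the imputation model, as SAP 5.3 allows.

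**SAP 7.3.4:** reconcile objective 6a, the outcome line and the adjustment line by stating the response times for the fourth and fifth secondary analyses. If they are 2 and 24 weeks, as objective 6a asks, drop 2-week ThDP from those two mixed models only and keep it in the 24-week treatment-comparison regressions. If the authors intend 24 weeks only, the covariate may stay, but the time term no longer fits and the 2-week part of the objective goes unanswered.

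**Cost:** wording only, with no change to data collection. For Mullen, some precision is given up if there truly is no 12-week effect: under the assumed correlations the 24-week residual SD is larger by a factor of √(0.96/0.897) = 1.03 to √(0.96/0.640) = 1.22, and power is 82% instead of 85–94%.

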7.3.10 VPC novelty score and attention and processing speed subscales

Outcome: Continuous outcomes of VPC novelty score and the attention and processing speed subscales at 24 and 52 weeks postpartum.

Primary analysis: Test for a treatment effect using a separate linear regression model for each outcome and estimate a difference in means (positive control minus placebo).

Adjustment: Hammersmith at 2 weeks postpartum and health centre

7.3.11 Language Preference Task score

Outcome: Continuous outcome of Language Preference Task score at 24 weeks postpartum.

Primary analysis: Test for a treatment effect using a linear regression model and estimate a difference in means (positive control minus placebo).

Adjustment: Hammersmith at 2 weeks postpartum and health centre

7.3.12 Oculomotor scores

Outcome: Continuous outcome of Oculomotor scores at 24 weeks postpartum. This outcome is expected to follow a skewed distribution and hence a log or other appropriate transformation will be applied prior to analysis.

Primary analysis: Test for a treatment effect using a linear regression model and estimate a difference in means (positive control minus placebo).

Adjustment: Health centre

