9.9 Cognitive assessments

We will conduct cognitive assessments at 2, 12, 24, and 52 weeks postnatal; video-recordings of data collection will be collected to aid in analysis. We will conduct the Hammersmith Infant Neurological Exam (10 minutes), an oculomotor exam (2 minutes), Infant Mullen Scales of Early Learning (10 minutes at 2 and 12 weeks postnatal, 15 minutes at 24 and 52 weeks postnatal), Caregiver Reported Early Development Instruments (CREDI; 15 minutes), a Primary Engagement Task (3 minutes; 2, 12, and 24 weeks only), a Secondary Engagement Task (2.5 minutes), the Visual Paired Comparison Task (7 minutes), and the Language Preference Task (6 minutes), in the women's home. See Figure 1 for the timepoints at which these tasks are conducted. At 52 weeks postnatal, we will also incorporate the Mother-Infant Free Play Interaction (5 minutes), and the MacArthur-Bates Communicative Development Inventory (8 minutes).

The Hammersmith Infant Neurological Exam is a standard tool for providing basic information about infants' neurological status through use of gentle touch and gentle social interaction in order to examine infants' sensory and motor responses; it has previously shown excellent interobserver reliability even among less experienced staff (53). An oculomotor exam was included because oculomotor disturbances are not uncommon among thiamine deficient adults (54). The Infant Mullen Scales of Early Learning is an individually administered, multi-domain measure of early development, with scales measuring development in visual reception, fine motor, gross motor, receptive language, and expressive language (55). The CREDI is a caregiver-reported measure of child development that has been shown to have right validity and reliability in low-resource settings (56). The Primary Engagement Task measures individual variation in infant, caregiver, and dyad-level developmental change in the ability to engage contingently with the partner in direct positive mutual engagement interactions. The Secondary Engagement Task measures individual variation in caregiver and infant ability to engage mutually in relation to an external object. The Visual Paired Comparison task (VPC; 5 minutes) and the Language Preference Task (5 minutes). The VPC probes infants' recognition memory and attention, and has been used to predict subsequent verbal IQ in

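### The oculomotor comparison is the only cognitive outcome adjusted for no earlier infant score; no reason is given, and some precision may be lost

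*Combined protocol and SAP*

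**What the plan says.** SAP 7.3.12 gives the outcome as "Continuous outcome of Oculomotor scores at 24 weeks postpartum", expects it to be skewed, and plans a log or other transformation. The 10 mg and 0 mg groups are compared by linear regression. The whole covariate list reads "Adjustment: Health centre".

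The neighbouring section, 7.3.11 (Language Preference), has "Adjustment: Hammersmith at 2 weeks postpartum and health centre". Section 7.3.10 (VPC) uses the same two covariates, and 7.3.9 (Mullen) uses the Mullen scales at 2 and 12 weeks with health centre.

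Protocol section 11 describes treatment-group comparisons as "adjusted for randomization strata and levels at 2 weeks postnatal". That sentence is about linear mixed-effects models for repeated measurements. SAP 5.6 requires health centre in all adjusted analyses and adds 2-week variables for some outcomes only, chosen in advance.

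On data collection, protocol section 9.9 says "We will conduct cognitive assessments at 2, 12, 24, and 52 weeks postnatal" and lists the oculomotor exam in the battery. It then refers the reader elsewhere for the detail: "See Figure 1 for the timepoints at which these tasks are conducted". Figure 1 is not reproduced in the text available for review.

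**The concern.** Four cognitive outcomes are compared between the same two arms. Three carry an earlier infant score and one does not, and the SAP leaves the difference unexplained. A pre-treatment infant measure is available: the SAP itself uses the 2-week Hammersmith score for two of the outcomes. The 2-week visit is the baseline visit (SAP 6.2), and the first blister pack is handed out then (protocol 8.3). A score from that visit is therefore a legitimate covariate.

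At stake is the width of one confidence interval for a secondary outcome. If the 2-week score predicts the 24-week oculomotor score, adjusting for it removes chance imbalance between the arms and narrows the interval. There is also a side benefit. SAP 5.3 guarantees a place in the imputation model to covariates pre-specified for adjustment, whereas other variables enter only as unnamed auxiliaries.

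**Working it through.** **Step 1: the four cognitive outcomes side by side.**

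| SAP section | Outcome | Earlier infant score in the model | Health centre |
|---|---|---|---|
| 7.3.9 | Mullen, composite and subscales | Mullen at 2 and 12 weeks | yes |
| 7.3.10 | VPC scores | Hammersmith at 2 weeks | yes |
| 7.3.11 | Language Preference | Hammersmith at 2 weeks | yes |
| 7.3.12 | Oculomotor | none | yes |

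**Step 2: the plan's own figures.** The documents give no effect size, SD, power or sample size for the oculomotor score. The stated trial size is for milk thiamine (SAP 3.6). A two-sample t-test with difference 40 µg/L, SD 43 µg/L, two-sided alpha 0.0083 and 90% power needs 38 per group; 38/0.80 = 47.5, so 48 per group and 4 × 48 = 192 in all. That reproduces the plan, and this point does not touch it.

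**Step 3: inputs for the oculomotor comparison.**
- Infants per arm: 80 (SAP 3.6), or 80 × 0.80 = 64 after 20% attrition.
- Two-sided alpha 0.05 (SAP 7).
- Eight health centres, so 7 degrees of freedom for centre.
- Within-centre correlation r between the 2-week score and the transformed 24-week outcome: not in the documents, so assumed over a range.

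**Step 4: formula.** Adding one baseline covariate multiplies the variance of the group difference by 1 − r² and its standard error by √(1 − r²). Power is for an effect that has 80% power without the covariate (noncentral t). The last two columns give the difference, in SD units, detectable with 80% power.

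| r | 1 − r² | √(1 − r²) | Fall in SE | Power | Detectable, 80/arm | Detectable, 64/arm |
|---|---|---|---|---|---|---|
| 0 | 1.00 | 1.000 | 0% | 80.0% | 0.446 | 0.499 |
| 0.1 | 0.99 | 0.995 | 0.5% | 80.4% | 0.444 | 0.497 |
| 0.2 | 0.96 | 0.980 | 2.0% | 81.6% | 0.437 | 0.489 |
| 0.3 | 0.91 | 0.954 | 4.6% | 83.6% | 0.425 | 0.476 |
| 0.5 | 0.75 | 0.866 | 13.4% | 89.9% | 0.386 | 0.432 |

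**Step 5: cost.** Residual degrees of freedom drop by one: from 160 − 2 − 7 = 151 to 150 with 80 per arm, and from 128 − 2 − 7 = 119 to 118 with 64. Estimating the extra slope raises the expected variance by about 1/149 = 0.7% or 1/117 = 0.9%. At r = 0.1 the net variance factor is 0.99 × 1.007 = 0.997 or 0.99 × 1.009 = 0.999, which is roughly break-even. Below that the covariate costs slightly more than it returns; above it the balance turns favourable.

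**The case against.** The strongest reply is that the SAP does what its own rules allow. SAP 5.6 makes only health centre compulsory and reserves 2-week covariates for some outcomes. Protocol section 11 writes its adjustment rule for repeated-measures mixed models, whereas the oculomotor analysis is a regression at a single time point, and the same section defers to the SAP. A reader might infer that the SAP contradicts the protocol. The documents do not support that: VPC and Language Preference do not adjust for their own 2-week level either. What remains is an unexplained difference. The SAP does carry 2-week adjustment into single-time-point regressions, for maternal ThDP and TKac in 7.3.4 and 7.3.5, so the type of model does not explain the omission.

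A reader might also infer that an oculomotor score is collected at 2 weeks and left unused. Section 9.9 lists the exam among tasks run over four visits, and only the Primary Engagement Task has its visits restricted in the text, but the task-by-visit grid is in Figure 1. The SAP may use an outcome's own baseline where one exists (Mullen) and a substitute where none does. On that reading, oculomotor might have no 2-week score. Only the Hammersmith and Mullen scores are confirmed at 2 weeks.

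Finally, the gain may be small. The confirmed candidate is a different instrument, predicting a skewed score 22 weeks later, and nothing in the documents supports a correlation of 0.3 or 0.5. That objection stands, and it limits the size of the claim.

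**Conclusion.** The point holds as a minor matter of efficiency and consistency on a secondary outcome. Oculomotor is the only cognitive outcome with no earlier infant score in its model, the SAP gives no reason, and a suitable pre-treatment score is collected.

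It would be wrong to infer that the planned comparison is invalid. Leaving out a prognostic covariate neither biases a randomised difference in means nor inflates its type I error. It would also go too far to say that precision is lost. The loss ranges from nil (r near 0) to about 13% of the standard error (r = 0.5), and the documents do not locate r in that range. The figures assume a linear relation on the transformed scale, a common slope in both arms, and 64 to 80 infants per arm.

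**What to change.** Before the database is locked and unblinded, replace the covariate line in SAP 7.3.12 with the one already used in 7.3.11: "Adjustment: Hammersmith at 2 weeks postpartum and health centre". If Figure 1 confirms an oculomotor exam at 2 weeks, use the 2-week oculomotor score in place of Hammersmith, with the same transformation as the outcome, and keep health centre. Only a 2-week score should be added, because a 12-week score is measured after treatment has begun.

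If the team prefers health centre alone, a sentence giving the reason would settle the inconsistency. Either way, protocol section 11 could state which comparisons its 2-week adjustment covers.

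Timing matters because the oculomotor exam is not among the video-coded tasks held back from the locked database (SAP 4.2), so a covariate chosen after unblinding would be open to challenge. The cost is one line of SAP text, no new data and one degree of freedom.
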